9.1.3.1 Analysis Period

In general, the analysis will be performed at a visit(s) level but in the case where data is collected more frequently for example the Mhealth or exercise training data we define the analysis period by month. Here, Week 1 is the period between V3 and V4, Month 1 is described as the period between V5 up to the date of V14, Month 2 is the day after V14 and until the date of V28 and Month 3 represents the day after V28 until the date of V43.

For certain endpoints (see section 9.6.1.2) related to $VO2_{max}$ and exercise capacity the analysis period Week 1 and Month 3 will have different baseline values dependent on the subject's product use group during the corresponding period for the calculation of the descriptive statistics.

9.1.4 Handling of Dropouts, Missing Data (Including Outside the Limits of Detection or Quantification) or Partial Data

Dropouts (discontinued subjects) and other subjects with missing data will be analyzed in the analysis set(s) when data are available, without imputation of missing data.

No imputation schemes for missing values will be applied.

For laboratory parameters outside the limit of detection or quantification, the following imputation will be performed:

- Values below the lower limit of detection (LLOD) or quantification (LLOQ) will be imputed as 0.5 x LLOD or LLOQ.
- Values above the upper limit of detection (ULOD) or quantification (ULOQ) will be imputed as the ULOD or ULOQ.

The number of values below LLOD (or LLOQ) or above ULOD (or ULOQ) will be presented in each summary table, as well as the statistics on the other quantitative values.

However, if 50% or more data are below the lower limit or above the upper limit, only the number of values below the lower limit and above the upper limit will be reported in the

Confidentiality Statement

Philip Morris Products SA.	Statistical Analysis Plan	Confidential
P1-EXC-01-EU	Final 2.0	Page 36 of 71
Related to PMI-RRP-WKI-112487		

summaries, together with minimum (if no value below the lower limit is present) and maximum (if no value above the upper limit is present) of the observed values, and no other statistics will be reported.

There will be no imputation of missing laboratory parameters.

For product use data that are missing:

• There will be no imputation and all available data (ePRO and/or paper) will be analyzed as is.

For bike training data that is incomplete:

A bike training session is defined as being complete if a subject trained for at least 20 minutes, if the training stop time is not available then the training session is taken as not done.

For heart rate data that was incomplete (<80 %) during V5, V14, V29 and V41 will be flagged and not used in the analysis of % of time spend at maximum heart rate. This will be flagged by using the protocol deviation description "Recording of HR is less than 32 min …".

9.1.5 Handling of Unplanned Data

The following rule will be applied to handle unscheduled visits: In the case of unscheduled measurements prior to randomization, the last value before randomization will be considered as baseline value. In all other cases, the unscheduled value will not be used for descriptive statistics as long as a corresponding scheduled value is available. Unscheduled measurements will be included (and marked) in the listings.

9.1.6 Handling of Mhealth Data

For Mhealth parameters, all data will be analyzed as is and no imputation will be performed. However, the first and last day will not be used in any analysis as the data may not be complete.

In addition, the following definitions will be used to define a valid day in terms of step count. Using the average of 5205 steps per day taken in Germany (Althoff, et al. 2017), we set a cutoff at approximately 20% and define a valid day as having more than or equal to 1000 steps. In a separate study on Multiple Sclerosis (MS) patients (Block, et al. 2017), a lower threshold of 300 steps was set to screen out patients who may not be wearing the device based on inspection of raw data.

Given that the Althoff study uses smart phones instead of a wearable device to track steps and is likely to underestimate the true step count since the phone may not be on the user all the

Confidentiality Statement

Data and information contained in this document are considered to constitute trade secrets and confidential commercial information, and the legal protections provided to such trade secrets and confidential information are hereby claimed under the provisions of applicable law. No part of this document may be publicly disclosed without the written consent of Philip Morris Products S.A
Philip Morris Products SA.	Statistical Analysis Plan	Confidential
P1-EXC-01-EU	Final 2.0	Page 37 of 71
Related to PMI-RRP-WKI-112487		

time. In addition, given that patients are likely to have lower step counts therefore a cut off of 1000 steps is reasonable. Therefore if a subject has less than 1000 steps recorded in a day, we assume that device was either not worn or worn for a limited time during the day and will not be used in any calculations related to the Mhealth device. In addition, for weekly based averages we will require 4 or more valid days per week with the starting day based on the date of randomization.

9.1.7 Handling of Implausible Data

For the activity minutes of MHealth data, if implausible values are present, for example, sedentary activity minutes more than 24 hours (1440 minutes) they will be excluded from the analysis. If the sum of the sedentary, active and very active number of minutes is more than 1440 minutes then all values will be excluded from the analysis.

For the waist circumference and weight data, if a percentage change from baseline of x% in one variable is not followed by a corresponding x/4% in the other then both would be included.

These observations will be flagged in the ADaM datasets.

9.1.8 Multiple Comparison/Multiplicity

As this study is exploratory in nature, no adjustments are made for multiplicity considerations. There will be no control of the overall type I error.

9.2 Disposition of Subjects

The disposition of subjects will be listed and summarized. The number and percent of subjects will be summarized for the following categories:

- Subjects screened
- Screen failures
- Enrolled, enrolled but not randomized
- Assigned to the Safety Set
- Randomized and further summarized for subjects:
 - Assigned to the FAS
 - Assigned to the AEECS
 - Assigned to the AEBECS
 - Completing the study
 - Discontinued (by primary reason).

Data and information contained in this document are considered to constitute trade secrets and confidential commercial information, and the legal protections provided to such trade secrets and confidential information are hereby claimed under the provisions of applicable law. No part of this document may be publicly disclosed without the written consent of Philip Morris Products S.A

Philip Morris Products SA.	Statistical Analysis Plan	Confidential
P1-EXC-01-EU	Final 2.0	Page 38 of 71
Related to PMI-RRP-WKI-112487		CAD DI EVO 01 EU

For screened subjects, only the total count (overall) but no percentage will be given. For screen failures, only the total count (overall) with percentage will be given. For randomized subjects counts and percentages will be provided by study arm and overall. Subject disposition will also be summarized at Visit 14 and Visit 28 to assess dropout rate.

9.3 Demographic and Other Baseline Characteristics

All demographic and baseline characteristics data will be listed and summarized for all analysis sets.

For the FTND score a frequency table according to the following classification will be provided by analysis sets:

- Mild 0 3
- Moderate 4 6
- Severe 7 10

No nesting of the two grouping variables sex and cigarette consumption at V1 is planned.

9.4 Measurement of Product Compliance

There is no restriction on allocated product use.

Although subjects are being requested to use solely the product allocated to their respective study arm, it is considered that not all subjects randomized to the IQOS arms or to the cigarette arm will exclusively use the randomized product at all times during the study. Subjects may concomitantly use IQOS and cigarettes (dual use). To account for dual use of IQOS and cigarettes, adjustments for cigarette or IQOS use outside of the intended arms will be done statistically. Similarly, it is expected that subjects in the SA arm who should stay abstinent during the study may relapse to the use of tobacco or nicotine-containing tobacco products (e.g., cigarette or IQOS). In addition to the randomized arms of IQOS, Cigarette or SA , additional arms comprising of the categories Dual-1 and Dual-2 according to the definition in Section 9.1.1 "Stratified Presentation" will be used in part of the analysis. Subjects in the 'Others' product use group (Figure 2) will only be listed and not analyzed.

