### 6.3.4 Stopping rules for Investigational Product

For safety purposes, use of the IP should be temporarily reduced or stopped in the event of any signs suggesting nicotine overexposure, e.g., gastrointestinal disturbance (nausea, vomiting, diarrhea, stomach, or abdominal pain), cold sweats, headache, dizziness, and breathing problems or any reasons at the discretion of the Investigator.

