### 12.4.3 Safety Set

The Safety Set consists of all subjects enrolled with signed ICF who have at least one valid safety assessment during the course of the study. The Safety Set will be analyzed by actual exposure (product use exposure).

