Missing data for self-reported daily use will not be imputed and we will assume that the derived average monthly use from non-missing data is representative of the actual usage. For each analysis period (Week 1 or Overall), if more than 50% of product use data is not available then the subject will be grouped into the 'Others' product use arm. Therefore, it is possible that a subject is not considered for statistical modelling as it is grouped into 'Others' for Week 1 (3 out of 7 days of product use data only) but available for analysis for the entire study period if more than 50% of product use data was eventually collected throughout the study. A subject may have switched product use groups throughout the study and the total number of subjects in an arm may fluctuate over time depending on the actual product use.

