8.2 Safety Set

The Safety Set consists of all subjects enrolled with signed ICF who have at least one valid safety assessment during the course of the study. The Safety Set will be analyzed by actual exposure (product use exposure, actual study arm).

Confidentiality Statement

Philip Morris Products SA.	Statistical Analysis Plan	Confidential
P1-EXC-01-EU	Final 2.0	Page 31 of 71
Related to PMI-RRP-WKI-112487		SAD DI EVC OI EU

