9.1.1 Stratified Presentation

Stratification criteria for the evaluation are:

- Randomized study arm Cigarette, IQOS-1, smoking abstinence (SA), IQOS-2) randomized arm.
- Product use (actual arm) i.e. actual product use exposure categorized based on self-reporting and biochemical verification according to Section 5.5.1 "Product Use Pattern":

Confidentiality Statement

Data and information contained in this document are considered to constitute trade secrets and confidential commercial information, and the legal protections provided to such trade secrets and confidential information are hereby claimed under the provisions of applicable law. No part of this document may be publicly disclosed without the written consent of Philip Morris Products S.A

Philip Morris Products SA.	Statistical Analysis Plan	Confidential
P1-EXC-01-EU	Final 2.0	Page 34 of 71
Related to PMI-RRP-WKI-112487		SAP_P1-EXC-01-EU

- o Cigarette,
- o IQOS-1,
- Smoking Abstinence (SA),
- IQOS-2,
- Dual users considered for IQOS-1 (Dual-1),
- Dual users considered for IQOS-2 (Dual-2),
- Cigarette consumption at V1 (10 to 19 cigarettes, more than 19 cigarettes per day)
- Sex (male, female)
- Age (<50, ≥ 50 years i.e. $21 \le Age < 50$ and $50 \le Age \le 65$])

The main stratification criterion for the evaluation is the actual product exposure, whereas data will be listed by randomization arm.

Further stratification by cigarette consumption and sex will be done for the analysis of VO_2max and exercise capacity and where explicitly defined. Further stratification by age and BMI will be done only where explicitly defined (e.g. for demographic data).

The AEECS, AEBECS and the Safety Set will be analyzed by actual study arm (product use exposure). The FAS will be analyzed by randomized study arm.

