9.6.4 Safety Evaluation

9.6.4.1 Adverse Events

AEs (including SAEs) will be collected from the time of ICF signature until the EOS for all enrolled subjects. Information recorded will include: verbatim description of the AE/SAE, start and stop dates, seriousness, severity (intensity), relatedness (to IP and study procedures), expectedness, action taken (e.g., whether or not the AE/SAE led to the subject's withdrawal from the study), and outcome (e.g., resolved, stabilized).

Adverse events which occur during the screening period will be listed together with corresponding information.

Adverse events (AEs) will be coded using the MedDRA® dictionary.

A summary showing the overall number of AEs, SAEs, severity, expectedness, relatedness, AE leading to death, AE leading to action taken and treatment given for an AE will be presented.

The frequency of AEs and number (and percentage compared to total) of subjects for each AE will be determined within each study arm and for all study arms. This will be done for a given AE with respect to the system organ class (SOC) and preferred term according to MedDRA® will be determined within each study arm and for all study arms (total) and tabulated. Tabulation will be sorted by the decreasing frequencies within the system organ classes and preferred term (within the system organ class).

The frequencies of the severity (intensity) and relationship to study procedures and IP, expectedness, for each adverse event will be tabulated for each study arm by SOC and preferred term.

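### SAP 9.4 makes no exception for safety when it lists 'Others' subjects without analysing them, so some Safety Set members have no assigned column in the safety tables

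*SAP*

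**What the plan says.** **Who is in the Safety Set.** SAP 8.2 and Protocol 12.4.3 define it as "all subjects enrolled with signed ICF who have at least one valid safety assessment". Neither randomisation nor a completed diary is required.

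**How it is grouped.** SAP 9.1.1: "The AEECS, AEBECS and the Safety Set will be analyzed by actual study arm (product use exposure". That section names six product-use categories: Cigarette, IQOS-1, SA, IQOS-2, Dual-1 and Dual-2. In SAP 13.2 the haematology, chemistry, urinalysis and vital-sign tables on the Safety Set are titled by product use category.

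**Who becomes 'Others'.** SAP 5.5.1: "if more than 50% of product use data is not available then the subject will be grouped into the 'Others' product use arm". The rule is applied separately to Week 1 (V3 to V4) and to Overall (V3 to V43, or to the last visit before early termination). When the electronic and paper diaries give different values for the same date, that date is treated as missing.

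**What happens to 'Others'.** SAP 9.4: "Subjects in the 'Others' product use group (Figure 2) will only be listed and not analyzed". SAP 9.6.1.2, by contrast, puts 'Others' beside Dual-1 and Dual-2 in a second group of descriptive tables. That section covers non-safety endpoints in the AEECS.

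**What the safety tables show.** SAP 9.6.4.1 plans an overall summary of adverse events, and frequencies that "will be determined within each study arm and for all study arms (total) and tabulated". The sections on serious adverse events, events leading to withdrawal, device events and laboratory values use the same arm-plus-total layout.

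**The concern.** The Safety Set is defined to include everyone, but it is displayed through a classification that does not include everyone. A subject with a sparse or discordant diary belongs to the set. Yet the only category open to that subject is one that SAP 9.1.1 does not name and SAP 9.4 says is not analysed. A diary problem is a reason not to attribute a subject to a product. It is no reason to leave that subject's adverse events out of the tables.

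At stake is whether the counts and denominators in the safety tables describe the set named in their titles (objective 11). Two programmers working from this SAP could produce different adverse event totals, and both could claim to have followed it. The gap would be hard to see in the output: in SAP 13.2, the table of analysis-set sizes by arm covers AEECS, AEBECS and FAS but not the Safety Set, and no demographic table for the Safety Set is listed.

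**Working it through.** The plan gives no figure to reproduce here. The check follows three kinds of subject through the rules.

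**1. Sparse diary.** The share missing is (days in period − days reported) / days in period, and the subject is 'Others' if it exceeds 0.50.
- Week 1, 3 of 7 days reported: (7 − 3)/7 = 57.1%, so 'Others'. This is the SAP's own example.
- Week 1, 4 of 7 days reported: (7 − 4)/7 = 42.9%, so a named category is kept.
- Overall, taking the nominal 106 days from V3 to V43: 'Others' if fewer than 0.5 × 106 = 53 days are reported.

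Once in 'Others', the subject is in the Safety Set (8.2), the set is shown by product-use category (9.1.1), 'Others' is not a listed category (9.1.1), and 'Others' is listed only (9.4). Read literally, no column results.

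**2. Discordant diaries.** A subject who filled in both diaries fully, but with different values on 4 of the 7 days, has those 4 days set to missing: 4/7 = 57.1%. A subject with complete records can therefore reach 'Others'.

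**3. Enrolled, never randomised.** Enrolment is at V2 and the exercise capacity test follows at the same visit (Protocol 9.2), so a procedure-related event before randomisation is possible. Both product-use periods start at V3, so no category exists for this subject. SAP 9.2 counts such subjects in disposition; SAP 9.6.4 gives them no column. This gap comes from 5.5.1 and 9.1.1, not from the sentence in 9.4.

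**Which period applies to safety.** SAP 5.5.1 says a subject can be 'Others' for Week 1 and in a named group for Overall. SAP 9.6.1.2 ties baselines to one period or the other, but only for non-safety endpoints. SAP 9.6.4 does not say which category a safety table uses, so even who lacks a column is not fixed.

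**Basis of the category.** SAP 9.1.1 mentions biochemical verification, but the section it cites (5.5.1) uses diary data in its text, and SAP 5.5 calls the biomarker refinement exploratory. In substance the grouping rests on the diary.

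**Sensitivity, under assumption.** The number of subjects in 'Others', k, is unknown. For illustration only, take 90 randomised subjects, an event with an assumed 2% incidence, and the chance that the named columns show at least one such event, 1 − 0.98^(90 − k):
- k = 0: 83.8%
- k = 1: 83.4%
- k = 5: 82.0%
- k = 10: 80.1%
- k = 15: 78.0%

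No value of k is supported by the documents. A single subject can still matter at a threshold. If 5 of 90 subjects have an event (5.6%) and one of them is left out of both numerator and denominator, the result is 4/89 = 4.5%. That falls below the 5% cut-off of the frequent-event table (15.2.3.1.9), if the cut-off is applied to the total; the table title does not say.

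**The case against.** The best defence is that 'not analyzed' means not modelled. SAP 5.5.1 describes the consequence of being 'Others' as exclusion from statistical modelling. SAP 9.6.1.2 then tabulates 'Others' descriptively, so the SAP does not itself apply the 9.4 sentence to every table, and safety is descriptive throughout. SAP 5.5.1 even calls 'Others' a product use arm, so an all-arms total could include it. As-exposed grouping of safety is prespecified in the protocol, and the study tests no hypotheses.

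Much of this stands, and it rules out some stronger readings that a reader might infer.
- *That these events vanish from every safety summary.* The plan includes an overall adverse event summary and an all-arms total on the Safety Set, and no sentence removes anyone from that total. Adverse events, serious adverse events, deaths and device events are all listed for the Safety Set.
- *That discontinuations are lost.* SAP 9.2 summarises them by primary reason, by study arm and overall, and Table 15.2.1.2 covers the FAS, which is grouped by randomised arm.
- *That the planned 20% dropout measures the loss.* For a subject who leaves early, the Overall period ends at the last visit before termination. Leaving early shortens the period and does not by itself create missing days.
- *That events under Protocol 6.3.4, where "use of the IP should be temporarily reduced or stopped in the event of any signs suggesting nicotine overexposure", would be counted against another product.* That depends on the category thresholds in Figure 2, which was not available for this review, and on averaging over the whole period.

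The subjects also remain visible elsewhere: recording less than half of the product use questionnaires is a major deviation (SAP 8.5.1), and deviations are listed and summarised for the Safety Set.

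What the defence does not do is settle the matter. It shows that 9.4 can be read more narrowly. It does not supply the exception, a column, or a definition of the total.

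**Conclusion.** The point holds as a defect in a stated rule. SAP 9.4, taken at its word, leaves Safety Set members in 'Others' without a column in the safety tables, and it conflicts with 9.6.1.2. Enrolled but never randomised members have no column for a separate reason. Whether either group counts in the safety total is left open.

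The size cannot be computed. It depends on how many subjects have more than half of their diary missing or discordant and how many are enrolled without being randomised, and the documents give neither. The 2% event rate and the values of k above are assumptions, used only to show direction. The conclusion rests on the text of SAP 5.5.1, 8.2, 9.1.1, 9.4 and 9.6.4; since Figure 2 is not shown, other routes into 'Others' could not be checked.

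**What to change.** 1. In SAP 9.4, limit the sentence on 'Others' to the model-based non-safety analyses, and make it agree with 9.6.1.2.
2. In SAP 8.2 and 9.6.4, state that the total column of every safety table is the whole Safety Set.
3. Add to the safety tables an 'Others' column and an 'enrolled, not randomised' column, both counted in the total.
4. State whether the Week 1 or the Overall category assigns a subject to a safety column.

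An adverse event overview by randomised arm, beside the as-exposed tables, would be a useful low-cost addition but is optional.

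The cost is SAP wording and extra table columns. No new data are needed.

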9.5 Extent of Exposure (Product Consumption)

The number of HeatSticks, cigarettes, or/and other tobacco and nicotine-containing products used for each subject will be listed by day. Summary statistics of HeatSticks, cigarettes, or/and

Data and information contained in this document are considered to constitute trade secrets and confidential commercial information, and the legal protections provided to such trade secrets and confidential information are hereby claimed under the provisions of applicable law. No part of this document may be publicly disclosed without the written consent of Philip Morris Products S.A

Philip Morris Products SA.	Statistical Analysis Plan	Confidential
P1-EXC-01-EU	Final 2.0	Page 39 of 71
Related to PMI-RRP-WKI-112487		CAD DI EVC AL EU

other tobacco and nicotine-containing products used will be presented by month and over the entire study for the AEECS, AEBECS and FAS by study arm.**Planned Statistical Analyses**

